## SYNOPSIS

Study Title	Remote electrical neuromodulation for acute procedural pain in chronic migraine patients receiving onabotulinumtoxinA
Objectives	To assess the effectiveness of remote electrical neuromodulation with the Nerivio ® device at relieving acute procedural pain in patients receiving onabotulinumtoxinA per PREEMPT protocol for chronic migraine prevention.
Study Period	24 weeks
Subjects	80 subjects ages 18 - 75 who meet criteria for chronic migraine receiving onabotulinumtoxinA for chronic migraine
Study Treatment	Nerivio ® (Remote Electrical Neuromodulation) applied to the upper extremity prior to the procedure and removed following procedure.
Study Design	Single-center, randomized, single-blind, sham-controlled, crossover study to evaluate the effectiveness of Nerivio ® for treatment of acute procedural pain in patients receiving onabotulinumtoxinA for the treatment of chronic migraine. During phase 1, 80 adults with a diagnosis of chronic migraines will be surveyed on their pain levels during routine procedure and then randomized to receive either intervention vs sham treatment at week 12 +/- 7 days (buffer time to accommodate rescheduling) for phase 2. For phase 3, subjects will then transition to receive the alternate therapy at week 24 +/- 7 days. Pain levels will be compared across time points
Inclusion and Exclusion Criteria	
Inclusion Criteria
 
 
1. Adults aged 18 to 75 years old
 
2. Meet the criteria for 1.3 chronic migraine based on ICHD3 criteria
 
3. Currently receiving onabotulinumtoxinA per PREEMPT protocol for the treatment of chronic migraine
 
4. Patient is willing and able to comply with the protocol to the satisfaction of the investigator
 
5. Patient has the capacity to provide written, informed consent for themselves
 
 
Exclusion Criteria
 
 
1. Participants with an active implanted electrical and/or neurostimulator device (e.g., cardiac pacemaker, cochlear implant).
 
2. Participants with congestive heart failure (CHF), severe cardiac or cerebrovascular disease.
 
3. Participants with uncontrolled epilepsy.
 
4. Pregnant, trying to get pregnant or breastfeeding female participants
 
5. Subjects participating in any other interventional clinical study.
 
6. Participants with other significant pain, medical or psychological problems that in the opinion of the investigator may confound the study assessments
 
7. Participants who have previous experience with the device
 
8. Patients with cranial deformities, prior cranial surgeries with violation of the calvarium, or shunt placement
 
9. Patients receiving concurrent nerve blocks or trigger point injections within the same visit
 

Measurements	Subjects will be surveyed on their pain intensity using a Visual Analog Scale pre-, intra- and post-procedure (approximately 0 – 5 minutes post-procedure). Additionally, patient demographic information (sex, age, race, ethnicity), BMI, arm circumference, depression/anxiety screen, medical comorbidities, headache qualities (location, duration, intensity, frequency, associated symptoms), previous rounds of onabotulinumtoxinA received, current treatment regimen (beyond onabotulinumtoxinA) including other preventive and abortive treatments will be recorded. Migraine-specific quality measures (MIDAS) will also be recorded throughout the study period. Patients will be contacted on the day following each treatment of onabotulinumtoxinA to follow-up on post-procedural headache.
Outcomes	
Primary: Pain intensity with a Visual Analog Scale, pre- , intra-, and post-procedure
 
Secondary:
 
 
1. Presence of post-procedural headache
 
2. Any adverse events.
 

CONFIDENTIAL: This document is the intellectual property of [name]. Acceptance of this document constitutes the agreement by the recipient that no unpublished information contained herein will be published or disclosed without prior written approval.

## 1. Background and Rationale:

Migraine is a condition that impacts a large segment of the global population (~958.8 million) and is exceeded only by stroke with regards to its overall burden of neurological disease (**GBD 2015 Neurological Disorders Collaborator Group**). It has been estimated that the prevalence of total migraine (episodic and chronic) is about 20.7% in women and 10.7% in men in the United States (**Burch 2020**). Of the patients with episodic migraine, it has been shown that around 2.5% will progress or “transform” into chronic migraine, defined as headache that occurs  $\geq 15$  days per month with at least 8 headaches with features of migraine based on the International Classification of Headache Disorders 3rd Edition (ICHD-3) criteria (**Buse 2012, see ICHD-3 criteria in supplemental material**).

The injection of onabotulinumtoxinA (BoNT-A) is common treatment for patients with a wide variety of conditions such as chronic migraine, cervical dystonia, spasticity, strabismus, neurogenic bladder, and hyperhidrosis. Proper implementation of this treatment modality can involve the injection of BoNT-A into many different sites per procedural visit and must be repeated to ensure continued effect. BoNT-A for the treatment of chronic migraine is administered per PREEMPT protocol, which involves the injection of 5U into 31 injection sites (total 155U) with the option for additional injections (up to 40-45U) based on a follow-the-pain strategy and must be administered every 10 to 12 weeks to maintain effect (**Aurora, 2010; Diener, 2010**). While levels of procedural discomfort do not appear to predict therapy continuation (**Anderson, 2020**), steps should be taken to reduce needle-related pain to minimize stress and anxiety surrounding the procedure.

Management of acute procedural pain is an area of considerable interest, typically with relation to pediatric populations. Many modalities have been found to be effective at reducing procedural needle-related pain, including immersive virtual reality distraction, cognitive-behavioral therapy, hypnosis, breathing interventions, clown therapy, and ethyl chloride spray; however, the effective implementation of these strategies tends to require hiring additional personnel or dedication of time that may not be feasible in a busy, clinical setting. The utilization of devices for management of acute procedural pain has been investigated for needle-related procedures in children (**Ballard, 2019**), but further investigation is required to understand the potential benefits of using for acute needle-related procedural pain in adults.

The Nerivio® device (Theranica Bio-Electronics Ltd., Israel) is a wearable, remote electrical neuromodulation (REN) device controlled by smartphone application that has been cleared for the acute treatment of migraine in adults and adolescents (**Yarnitsky 2019, Tepper 2020, Ailani 2022**). The proposed mechanism of action involves stimulation of peripheral nerves within the upper extremity, thereby inducing conditioned pain modulation (CPM) and reduction of acute pain. While this device is cleared for the treatment of paroxysmal pain in migraine, little is known about whether it could demonstrate effectiveness at reducing pain in the head and neck that occurs in response to procedural intervention. The aim of the current study is to compare acute procedural pain intensity among chronic migraine patients receiving Nerivio® vs sham device treatment during treatment with onabotulinumtoxinA per the PREEMPT protocol.

## 2. Objectives

The goal of this research proposal is to establish remote electrical neuromodulation with Nerivio® as an efficacious therapy for acute procedural pain in patients receiving onabotulinumtoxinA

CONFIDENTIAL: This document is the intellectual property of [name]. Acceptance of this document constitutes the agreement by the recipient that no unpublished information contained herein will be published or disclosed without prior written approval.

for the treatment of chronic migraine. We hope to demonstrate an improvement in procedural pain when patients receive remote electrical neuromodulation with Nerivio® compared to no treatment and sham treatment. We will record acute procedural pain utilizing a numerical 0-10 rating scale and will compare this number across phases to determine efficacy. We will test the hypotheses that: 1) Patients receiving transcutaneous remote electrical neuromodulation with Nerivio® will experience significantly lower levels of acute procedural pain compared to when they received either no treatment or sham treatment and that (2) patients receiving remote electrical neuromodulation with Nerivio® will experience a reduced incidence of post-procedural headache compared with either no treatment or sham treatment. For the purpose of the study, “post-procedural headache” will be defined as a headache 24-hours post-procedure in which head pain lasts 4 hours or more and is at least moderate in severity or during which abortive medications are used to treat the patient’s head pain.

We believe that enacting strategies to reduce acute procedural pain provides benefits for the patient experience and if results indicate that remote electrical neuromodulation provides significant benefits, this method of treatment may be considered for wider use where injection of local anesthetic is unable to be performed, contraindicated, or not feasible, e.g., onabotulinumtoxin for dystonia/spasticity or cosmetic use, electromyography, or acupuncture.

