**5.3. Treatment Phase**

Upon receipt of informed consent, the patient will enter phase 1 of the study. This phase is used to determine baseline experience with the PREEMPT protocol and will involve obtaining pre-, intra-, and post-procedural pain intensity levels based on a standard visual analog scale. Subjects will then be contacted the following day to inquire about the presence of post-procedural headache. Following their initial treatment of BoNT-A, subjects will then be randomized to receive either remote electrical neuromodulation with Nerivio® or stimulation with a sham device for their next BoNT-A treatment and enter phase 2. During phase 2, patients will again receive BoNT-A treatment via PREEMPT protocol at week 12 +/- 7 days (buffer period to accommodate rescheduling) and will also be treated with either Nerivio® or receive stimulation with a sham device supplied by **Theranica Bio-electronics, Ltd.** Patients will have the device applied 20 minutes prior to starting the Botox procedure with an estimated total time of wearing the device around 40 to 45 minutes. Again, patients will be surveyed regarding their pre-, intra-, and post-procedural pain intensity and will be contacted on the following day re: post-procedural headache. Finally, patients will receive their final treatment of BoNT-A at week 24 +/- 7 days and will receive concurrent treatment with the alternative stimulation setting (either Nerivio® treatment stimulation or sham stimulation). Pre-, intra-, and post-procedural pain levels and post-procedural headache will be recorded in an identical fashion.

CONFIDENTIAL: This document is the intellectual property of [name]. Acceptance of this document constitutes the agreement by the recipient that no unpublished information contained herein will be published or disclosed without prior written approval.

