## **7. Outcome Measures**

#### *7.1. Primary Outcome Measure*

The primary outcome is the reduction in pain intensity measured via Visual Analog Scale (VAS) among patients at the baseline or sham treatment compared to treatment with remote electrical neuromodulation using Nervio ®.

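### The objectives and the Section 7.1 primary outcome set no treatment beside sham as an efficacy comparator, but no treatment occurs only at the unrandomised first visit, and the power and models cover only REN versus sham

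*Combined protocol and SAP*

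**What the plan says.** Section 2 (Objectives) names two comparators throughout. The goal is improvement "compared to no treatment and sham treatment". Hypothesis 1 is that patients on REN "will experience significantly lower levels of acute procedural pain compared to when they received either no treatment or sham treatment". Hypothesis 2 is that they "will experience a reduced incidence of post-procedural headache compared with either no treatment or sham treatment". For the pain score, the investigators "will compare this number across phases to determine efficacy". Section 7.1 defines the primary outcome as a reduction in pain "among patients at the baseline or sham treatment compared to treatment with remote electrical neuromodulation". The outcome listed in the Synopsis names no comparator, although the Synopsis design paragraph ends by saying that pain will be compared across time points.

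Section 5.3 describes the visits. On phase 1 it says: "This phase is used to determine baseline experience with the PREEMPT protocol". No device is used at that visit. Randomisation comes afterwards: "Following their initial treatment of BoNT-A, subjects will then be randomized to receive either remote electrical neuromodulation", or else sham. Phase 3 gives the other device setting, so no later visit is device-free.

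The rest of the plan has one comparator. Section 1 gives the aim as "to compare acute procedural pain intensity among chronic migraine patients receiving Nerivio® vs sham device treatment". Section 7.3.1 powers the difference between treatment and sham in a 2x2 crossover. Section 7.3.2 specifies the linear mixed model for that 2x2 design, with treatment, sequence and period, and models headache in the same way. No test, model or power is given for a comparison with phase 1.

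**The concern.** The hypotheses and the Section 7.1 outcome promise an efficacy conclusion against no treatment. Phase 1 cannot supply it as a controlled comparison. Every subject has it first and nobody is randomised to it, so being untreated and being at the first visit are the same thing in these data. A difference between REN and phase 1 would combine the device-specific effect, the response to wearing any device, and whatever changes between the first and later procedures.

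Two things are at stake. First, if the sham comparison fails, a report could still point to the protocol's own primary outcome wording to present a fall from phase 1 as efficacy. Second, the documents do not settle whether REN must beat one comparator or both. The goal joins them with *and*; the hypotheses and Section 7.1 join them with *or*. If both are required, the power statement in Section 7.3.1 does not describe the hypothesis as written.

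**Working it through.** **Inputs from the documents.** Section 7.3.1: N = 80, 40 per sequence, standardised effect 0.45, two-sided 5%, power 80%. Section 5.3: phase 1 device-free, first and before randomisation; phases 2 and 3 REN and sham in random order.

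**Assumptions.** The documents give no SD, no correlation and no change between phase 1 and later visits. I take independent within-subject errors of equal SD, express effects in that SD, and ignore the interim look. All shift sizes are assumed.

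**1. The plan's own figure.** The standard error of REN minus sham is √(2/80) = 0.158. Noncentrality is 0.45 × √(80/2) = 2.846. The two-sided t-test on 78 df has power 80.3%. The stated 80% is reproduced, with 0.45 read as the difference over the within-subject SD.

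**2. What each contrast contains.**

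| Contrast | Visits used | Randomised order? | What it contains |
|---|---|---|---|
| REN − sham | phases 2 and 3 | yes | device-specific effect, adjusted for period |
| REN − no treatment | phase 2 or 3 against phase 1 | no | device-specific effect + placebo response + any change since the first visit |

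A larger sample does not separate the terms in the second row, because no subject is untreated at any other visit.

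**3. Power if both comparisons must succeed.** Both contrasts have variance 2/80 and share the REN visit, so their covariance is 1/80 and their correlation is (1/80)/(2/80) = 0.5. With a true effect of 0.45 on each and no shift from phase 1, the joint probability is 70.4% by the bivariate normal. Simulation of the two t-tests (200,000 trials) gives 69.0%.

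A general rise in pain after phase 1 shrinks the second contrast, for example to 0.45 − 0.10 = 0.35. A general fall enlarges it.

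| Assumed shift after phase 1 (within-subject SD) | Joint power |
|---|---|
| rise 0.30 | 15% |
| rise 0.20 | 32% |
| rise 0.10 | 53% |
| none | 69% |
| fall 0.10 | 77% |
| fall 0.20 or more (to 0.45) | 80% |

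**4. REN versus phase 1 with no device-specific effect (illustration).** Suppose pain falls by the same amount at both device visits. Noncentrality is the fall × √40, in a paired t-test.

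| Assumed shared fall | Noncentrality | REN versus phase 1 significant | REN versus sham significant |
|---|---|---|---|
| 0.10 | 0.632 | 9.6% | 5% |
| 0.20 | 1.265 | 23.9% | 5% |
| 0.30 | 1.897 | 46.6% | 5% |
| 0.45 | 2.846 | 80.3% | 5% |

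If both comparisons are required, false support for the device stays at or below about 2.5% in all four cases, because REN must still beat sham.

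No figures are given for post-procedural headache. The confounding with visit order is the same.

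**The case against.** The strongest reply is that the operative text already settles the matter. The aim, the power statement and the 2x2 model are all REN versus sham, and Section 7.3.2 plans no test against phase 1. That stands as far as it goes: no planned p-value, sample size or error rate is wrong. It does not remove the conflict, because Section 2 says that these hypotheses will be tested and Section 7.1 is the definition of the primary outcome.

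A second reply is that lower than either comparator ordinarily means lower than each, and the goal sentence supports this. I accept it as the natural reading. A reader might infer from the last table in the working that the trial carries a false-positive risk of up to 80%. The documents do not support that. It needs both an assumed fall and a rule that success against phase 1 alone is enough, and no section states such a rule.

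Third, the documents give no evidence of drift. Section 4.1 requires patients to be receiving onabotulinumtoxinA already, which weakens a first-exposure effect, and Sections 4.1 and 4.2 set no procedural-pain threshold, so entry selection gives no obvious regression to the mean. Bias from time effects is therefore possible, not shown.

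Finally, total benefit over no device may be of clinical interest, with placebo response counted as part of it. That is fair, but possible time and order effects would remain in the comparison.

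**Conclusion.** The point holds as a conflict between the stated objectives and primary outcome on one side and the design and analysis on the other. It should be fixed. The no-treatment comparison is fully confounded with visit order, and that follows from Section 5.3 without any assumption. The 69% joint power rests on equal effects of 0.45, no shift and independent errors of equal SD. The 10% to 80% range is illustration only and rests on assumed shifts.

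Two further readings should be set aside. A reader might infer that the 80% power or the planned analysis is wrong. The 80% reproduces, and REN versus sham in phases 2 and 3 is unaffected. A reader might also infer that the planned model cannot be estimated. That difficulty would arise only if phase 1 were added to the model with period as a category, and the plan does not propose this.

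**What to change.** - **Section 2.** Make sham the comparator in the goal and in both hypotheses. Replace the comparison across phases with: *between the REN and sham visits (phases 2 and 3) to determine efficacy*. No treatment may stay as a separate objective if it is labelled uncontrolled and non-confirmatory.
- **Section 7.1.** Remove baseline from the comparator, leaving sham treatment only.
- **Synopsis, Study Design.** Replace the last sentence with: *Pain levels at the pre-, intra- and post-procedure time points will be compared between REN and sham; phase 1 levels will be summarised descriptively.* This keeps the within-visit time points.
- **Section 7.3.2.** Add: *For the primary outcome, REN versus sham in phases 2 and 3 is the sole confirmatory contrast; post-procedural headache is secondary and uses the same REN versus sham contrast. Change from phase 1 will be reported descriptively, side by side for REN and sham, as an uncontrolled comparison.*

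The cost is wording, plus a confirmatory no-treatment claim that the design cannot support. Phase 1 data are still collected and shown. Sample size, randomisation, model terms and interim boundaries do not change.

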### **3. Preliminary Data**

The utilization of devices for acute procedural pain has been investigated in the past. One such device, the Buzzy®, relies on a vibrating motor and cold sensation to interfere with discomfort related to the procedure. A meta-analysis published in 2018 compiled the results of 9 studies (n=1138) and found that the device significantly reduced self-reported pain levels (standardized mean difference [SMD]: -1.11; 95% confidence interval [CI]: -1.52 to -0.70;  $P < 0.0001$ ), observer-reported pain levels (SMD: -1.19; 95% CI: -1.90 to -0.47;  $P = 0.001$ ), and procedural anxiety (SMD -1.37; 95% CI: -1.77 to -0.96;  $P < 0.00001$ ). The proposed mechanism of action of the Buzzy® device is the Gate Control Theory, whereby non-noxious stimuli interfere with the transmission of painful stimuli at the level of the dorsal horn of the spinal cord (**Ballard, 2018**).

The proposed mechanism of action of Nerivio® differs from the Buzzy® device. Per the device’s manufacturers, Nerivio® produces its effects via remote electrical neuromodulation (REN). REN acts by stimulating peripheral nerves of the upper extremity with electrical stimulus that is not painful. These signals induce a conditioned pain modulation (CPM) response at the level of the brainstem, specifically at the periaqueductal gray and rostral ventromedial medulla (**Yarnitsky, 2019**). Nerivio® has been found to be effective for the acute treatment of migraine headache compared to sham stimulation with significant benefits in pain relief (66.7% [66/99] vs 38.8% [40/103]; therapeutic gain of 27.9% [CI95%, 15.6-40.2];  $P < .0001$ ), pain-free (37.4% vs 18.4%,  $P = .003$ ), and most-bothersome-symptom relief (46.3% vs 22.2%,  $P = .0008$ ) at 2 hours post-treatment. The device also has device-related adverse events (4.8% [6/126] vs 2.4% [3/126],  $P = .499$ ) with the most common adverse events being warmth sensation (2.4% treatment vs 0.8% sham; redness 1.6% treatment vs 0.8% sham; and pain in the arm (1.6% treatment vs 0% sham) (**Yarnitsky, 2019**).

While this device has been studied for acute migraine, further studies are required to determine its effectiveness at treating other types of pain. Of interest to this study, we will be investigating acute procedural pain in the cranial-cervical region.

## **4. Patient Selection**

Subjects will be recruited from the patient population at the Headache Medicine clinic at the Mayo Clinic Scottsdale, Arizona location. Subjects will initially be approached in the clinic in person or by phone. Prior to study initiation, written informed consent or electronic consent will be obtained from the subject. Goal enrollment is 80 adults (18 - 75 years old) who meet the criteria for a diagnosis of chronic migraine that have been stable on their current headache medication for a minimum of 8 weeks. Definition of chronic migraines will be defined per the International Classification of Headache Disorders (ICHD3) as a headache occurring on 15 or more days/month for more than 3 months, which have the features of migraine headache on at least 8 days/month. Subjects should be approved and scheduled to received onabotulinumtoxinA for the treatment of chronic migraine for recruitment.

